3.5. Missing Data and Outliers

3.5.1. Missing Data

In general, missing data will not be imputed unless methods for handling missing data are specified.

For missing last dosing date of study drug, imputation rules are described in Section 3.7.1. The handling of missing or incomplete dates for adverse event (AE) onset is described in Section 7.1.5.2, and for prior and concomitant medications in Section 7.8.

For analyses of categorical HCV RNA data, missing posttreatment HCV RNA data will have the missing data imputed. Missing on-treatment HCV RNA will have the missing data imputed up to the time of the last dose (for on-treatment displays). If the study day associated with the last dosing date is greater than or equal to the lower bound of a visit window, and the value at the visit is missing, the value will be imputed. If the study day associated with the last dosing date is less than the lower bound of a visit window then the on-treatment value at that visit will remain missing.

If a data point is missing and is preceded and followed in time by values that are “< LLOQ target not detected (TND)”, then the missing data point will be set to “< LLOQ TND”. If a data point is missing and preceded and followed by values that are “< LLOQ detected”, or preceded by “< LLOQ detected” and followed by “< LLOQ TND”, or preceded by “< LLOQ TND” and followed by “< LLOQ detected”, then the missing value will be set to “< LLOQ detected”. In these situations the data point will be termed a bracketed success; otherwise, the data point will be termed a bracketed failure (ie, \geq LLOQ detected). If a data point is missing and is not bracketed, the missing data point will also be termed a failure (ie, \geq LLOQ detected) except for SVR24, which will be imputed according to SVR12 status. Success for SVR12 who have no further HCV RNA measurements collected will be counted as a success for SVR24 due to the high correlation between these 2 endpoints.

For the analyses of continuous HCV RNA efficacy data, when and only when a missing HCV RNA value is imputed as < LLOQ TND or < LLOQ detected according to the imputation rule described above, the corresponding continuous value will be imputed to LLOQ - 1 IU/mL. No other imputation will be performed for continuous HCV RNA data.

In the analysis of the PedsQL™ Pediatric Quality of Life Inventory V4.0 Short Form (SF15) questionnaire, missing data at on-treatment visits and posttreatment follow-up Week 12 (FU-12) visit will not be imputed. Last posttreatment observation carried forward will be used for imputation of missing data at posttreatment follow-up Week 24 visit.

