3.3. Virologic Response-Based Stopping Criteria

HCV RNA will be unblinded to the Investigator and Sponsor.

The following on-treatment virologic response-based treatment stopping criteria will be utilized:

- Confirmed HCV RNA \geq LLOQ after 2 consecutive HCV RNA $<$ LLOQ
- Confirmed $>1 \log_{10}$ increase from nadir
- HCV RNA \geq LLOQ through 8 weeks of treatment

Confirmation should be performed as soon as possible but within 2 weeks after determination of initial observation. Subjects that meet the virologic response-based stopping criteria above will be notified of their eligibility to participate in the Long-Term Follow-Up Study (GS-US-334-1113).

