9.2.2. Data Handling Conventions

Natural logarithm transformation for key PK parameters, such as C_{max} and AUC_{tau} , will be applied for pharmacokinetic analysis.

The PK concentration values below the limit of quantitation (BLQ) will be treated as zero for the determination of summary and order statistics. Individual values that are BLQ will be presented as “BLQ” in the concentration data listing and will be excluded in any calculation of geometric means or ratios. For the presentation of summary and order statistics, if at least 1 subject has a concentration value BLQ for the time point, then the minimum value will be displayed as “BLQ”. If more than 50% of the subjects have a concentration data value BLQ for the time point, then the minimum and median values will be displayed as “BLQ”. If all subjects have concentration data values BLQ for the time point, then all order statistics (minimum, first quartile [Q1], median, third quartile [Q3], maximum) will be displayed as “BLQ”.

Missing data can have an impact upon the interpretation of the trial data. Other than the endpoints discussed below, in general, values for missing data will not be imputed.

For the analysis of post-baseline categorical efficacy endpoints, if a data point is missing and is preceded and followed in time by values that are deemed successes, then the missing data point will be termed a success; otherwise the data point will be termed a failure.

Any subject with missing data due to premature discontinuation of the study medication will be considered a failure at the time points subsequent to the date of discontinuation. If no HCV RNA values are obtained after the last dose of study medication, the subject will be considered a treatment failure for the SVR endpoints.

Where appropriate, safety data for subjects that did not complete the study will be included in summary statistics. For example,

- If a subject received study medication, the subject will be included in a summary of adverse events according to the treatment received; otherwise, if the subject is not dosed then they will be excluded from the summary.
- If safety laboratory results for a subject are missing for any reason at a time point, the subject will be excluded from the calculation of summary statistics for that time point. If the subject is missing a pre-dose value, then the subject will be excluded from the calculation of summary statistics for the pre-dose value and the change from pre-dose values.

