9.6.2. Secondary Efficacy Analysis

For the PK Lead-in Phase, serum HCV RNA actual values and change from baseline will be summarized at each visit.

For the Treatment Phase, the proportion of subjects with HCV RNA below LLOQ over time (including SVR endpoints SVR4 and SVR24) will be presented in tabular and graphical form. In addition, descriptive summaries and listings will be provided for additional efficacy evaluations including serum HCV RNA actual values and change from baseline, proportion of subjects with virologic failures, and other endpoints of interest including ALT normalization.

PPD

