6.4. Changes From Protocol-Specified Efficacy Analyses

There are no changes from protocol-specified efficacy analyses.

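### SAP 3.5.1 leaves on-treatment HCV RNA missing after early stopping where Protocol 9.2.2 counts failure, and SAP 6.4 does not declare the change

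*SAP*

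**What the plan says.** **Protocol.** Section 9.2.2 sets the missing-data rules for post-baseline categorical efficacy endpoints. A child whose data are missing because study drug was stopped early "will be considered a failure at the time points subsequent to the date of discontinuation". The rule is not confined to SVR, since the next sentence gives a separate rule for the SVR endpoints. Section 9.6.2 includes "the proportion of subjects with HCV RNA below LLOQ over time" among the Treatment Phase efficacy results.

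**SAP.** Section 3.5.1 states: "Missing on-treatment HCV RNA will have the missing data imputed up to the time of the last dose", with a note that this is for on-treatment displays. When the last dose day is at or after the lower bound of a window, a missing value is imputed. When it is before the lower bound, "then the on-treatment value at that visit will remain missing". Post-treatment values are handled differently: "missing posttreatment HCV RNA data will have the missing data imputed".

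Section 6.2.1 lists the percentage below LLOQ by study visit as a secondary efficacy endpoint. Section 6.2.2 applies the 3.5.1 rules to it, with Clopper-Pearson 95% intervals by treatment group and a graph over time on treatment. Section 6.4 then says: "There are no changes from protocol-specified efficacy analyses".

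**Stopping rules.** Protocol 3.3 introduces the breakthrough, rebound and non-response criteria with "The following on-treatment virologic response-based treatment stopping criteria will be utilized". Section 3.4 makes meeting them a reason for mandatory discontinuation of study medication.

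**The concern.** The two documents give different answers to the same question: what is a child's on-treatment response status at a planned visit after drug has been stopped early? The protocol says failure. The SAP says no value, and says elsewhere that nothing has changed. A reader who knows the protocol would take the by-visit curve to describe all treated children.

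The missingness is also related to outcome. Virologic failure on treatment obliges the child to stop, so at least some of the children without a value at later visits would be those for whom treatment failed. If they leave the denominator, the percentage below LLOQ can rise from one visit to the next without any further child responding. What is at stake is one secondary efficacy display and its intervals, not the key efficacy result.

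**Working it through.** **Plan's own figures.** The plan gives no by-visit rate and no discontinuation rate. Its only computed efficacy figures are the SVR12 half-widths in SAP 1.3. These reproduce by normal approximation as 1.96 × √(0.9 × 0.1/N): 5.88% for N = 100 (stated 5.9%) and 5.37% for N = 120 (stated 5.4%). The present point does not rest on them, but the two planned group sizes are used below.

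**Inputs**
- N = 100 (12 to <18 years) and N = 120 (3 to <12 years), from SAP 1.3. N = 10 is an assumed small treatment group; SAP Table 3-1 splits the age groups by genotype, treatment experience, cirrhosis status and duration.
- The Week 12 window opens on Day 71 (SAP Table 3-4).
- d = children whose last dose is before the window opens. Assumed, shown over a range.
- r = children still on drug with HCV RNA at or above LLOQ. Assumed 0 or 2.
- Interval: two-sided 95% Clopper-Pearson (SAP 6.2.2).

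**Formulas**
- SAP rule, reading missing as excluded: (N − d − r)/(N − d).
- Protocol rule, early stop counted as failure: (N − d − r)/N.
- Gap: (N − d − r) × d / [N(N − d)], which reduces to d/N when r = 0.

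**Results at Week 12**

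| N | d | r | SAP rule, missing excluded (95% CI) | Protocol rule (95% CI) | Gap, points |
|---|---|---|---|---|---|
| 100 | 2 | 0 | 98/98 = 100% (96.3–100) | 98/100 = 98.0% (93.0–99.8) | 2.0 |
| 100 | 4 | 0 | 96/96 = 100% (96.2–100) | 96/100 = 96.0% (90.1–98.9) | 4.0 |
| 100 | 6 | 0 | 94/94 = 100% (96.2–100) | 94/100 = 94.0% (87.4–97.8) | 6.0 |
| 120 | 2 | 0 | 118/118 = 100% (96.9–100) | 118/120 = 98.3% (94.1–99.8) | 1.7 |
| 120 | 6 | 0 | 114/114 = 100% (96.8–100) | 114/120 = 95.0% (89.4–98.1) | 5.0 |
| 120 | 6 | 2 | 112/114 = 98.2% (93.8–99.8) | 112/120 = 93.3% (87.3–97.1) | 4.9 |
| 10 | 1 | 0 | 9/9 = 100% (66.4–100) | 9/10 = 90.0% (55.5–99.7) | 10.0 |

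On the exclusion reading, the SAP rate exceeds the protocol rate whenever at least one child stops early and at least one child still on drug is below LLOQ. With r = 0 it is 100% whatever d is.

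**If the denominator is the FAS instead.** A child with no value is not counted below LLOQ, so the SAP rate is also (N − d − r)/N and the gap is zero. The 3.5.1 exception therefore alters the percentage below LLOQ only if such children are excluded.

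**Timing of a Week 8 non-responder.** Week 8 is Day 56 ± 3, that is Day 53 to 59 (Protocol 6.4.3; SAP Table 3-4). Confirmation may take up to 2 weeks (Protocol 3.3), which reaches Day 67 to 73. The Week 12 window opens on Day 71, and samples up to 2 days after the last dose still count as on-treatment (SAP 3.7.2). Some non-responders would thus have no Week 12 value, while others would have an observed or failure-imputed one.

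**The case against.** The best counter-argument is that the SAP never says these children leave the denominator. It names exclusion explicitly elsewhere in 6.2.2: for continuous HCV RNA, and for ALT normalization, where the wording contrasts ALT with the HCV RNA below-LLOQ tables. SAP 3.1.2 also makes the FAS the primary efficacy set. This has some weight. It is not decisive, because the ALT contrast may concern imputation only, and because the exception in 3.5.1 would have no effect on the percentage under an FAS denominator. Exclusion remains the natural reading, but it is an inference.

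Second, an on-drug display is a legitimate and common choice, and 3.5.1 labels its rule as being for on-treatment displays. That is fair. It does not make the choice the protocol's, nor the no-change statement in 6.4 correct. Protocol 9.6.3 leaves details to the SAP, which is not licence for an undeclared reversal.

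Third, failures remain visible elsewhere. On-treatment virologic failure is summarised over the FAS (SAP 6.2.2), and SAP 4.1 reports early stopping with reasons. This stands, and it limits the consequence. So does the absence of any efficacy comparison (SAP 6.1.2).

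A reader might go further and infer that the by-visit curve is bound to climb towards 100% because the SAP removes the virologic failures. The documents do not support that. The denominator is unstated, some Week 8 non-responders may still have a Week 12 value, and a child who stopped for another reason while below LLOQ is a failure under the protocol rule without being a virologic failure.

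**Conclusion.** The contradiction between Protocol 9.2.2 and SAP 3.5.1 is explicit, and SAP 6.4 is wrong to report no change. Confidence in that is high.

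The size is less certain. If missing means excluded, the by-visit percentage below LLOQ is overstated relative to the protocol rule, by d/N when all children still on drug are below LLOQ. With 2 to 6 assumed stops that is 2 to 6 points for N = 100, and 1.7 to 5.0 points for N = 120; one stop in an assumed group of 10 gives 10 points. The documents supply no value for d. Some, not necessarily all, of the children removed would be virologic failures.

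The effect is confined to the on-treatment by-visit percentages, their intervals and the graph. SVR12, SVR4 and the virologic-failure table are unaffected. This is a minor to moderate point that should be corrected before the SAP is final.

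**What to change.** 1. In SAP 3.5.1 and 6.2.2, for the by-visit HCV RNA below-LLOQ table and graph, state that the denominator is the FAS. Count subjects who stopped study drug prematurely as at or above LLOQ at each later planned on-treatment visit of their assigned duration where data are missing, as Protocol 9.2.2 requires.
2. If the on-drug display is kept, label it supportive, and print its denominator and the number stopped at each visit.
3. If it is kept, list it in SAP 6.4 as a change from the protocol-specified efficacy analyses.

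The cost is a few lines of SAP text and one derivation flag, with no new data. If the programmed tables currently exclude these children, the later on-treatment percentages will become somewhat less favourable.

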3.5.2. Outliers

Outliers will be identified during the data management and data analysis process, but no sensitivity analyses will be conducted. All data will be included in the data analysis.

3.6. Data Handling Conventions and Transformations

By-subject listings will be presented for all subjects in the Safety Analysis Set and sorted by subject ID number, visit date, and time (if applicable) unless otherwise specified. Data collected on log forms, such as AEs, will be presented in chronological order within subject.

Age (in years) on the date of the first dose of study drug and sex at birth will be used for analyses and presentation in listings.

If a subject was not dosed with study drug at all, then the date the informed consent was signed will be used instead of the first dose date of study drug. For some countries, only birth year is collected on the eCRF. In those cases, “01 January” will be used for the unknown birth day and month for the purpose of age calculation, unless age is captured on the eCRF.

Non-PK data that are continuous in nature but are less than the lower limit of quantitation or above the upper limit of quantitation will be imputed as follows:

- A value that is one unit less than the limit of quantitation will be used for calculation of descriptive statistics if the datum is reported in the form of “< x” (where x is considered the limit of quantitation). For example, if the values are reported as < 50 and < 5.0, values of 49 and 4.9, respectively, will be used for calculation of summary statistics. An exception for this rule is any value reported < 1. For the values reported as < 1 or < 0.1, value of 0.9 or 0.09 will be used for calculation of summary statistics.
- A value that is one unit above the limit of quantitation will be used for calculation of descriptive statistics if the datum is reported in the form of “> x” (where x is considered the limit of quantitation). Values with decimal points will follow the same logic as above.
- The limit of quantitation will be used for calculation of descriptive statistics if the datum is reported in the form of “≤ x” or “≥ x” (where x is considered the limit of quantitation).

The COBAS[®] AmpliPrep/COBAS[®] TaqMan[®] HCV Test, v2.0 for use with the High Pure System was used to determine HCV RNA results in this study. The lower limit of quantitation (LLOQ) of the assay is 15 IU/mL.

When the calculated HCV RNA value is within the linear range of the assay, then the result will be reported as the “<< numeric value>> IU/mL”. This result will be referred to in this document as the numeric result or as “≥ LLOQ detected” for categorical result.

When HCV RNA is not detected, the result is reported as “No HCV RNA detected” or “target not detected”. This result will be referred to in this document as “< LLOQ target not detected” or “< LLOQ TND”.

When the HCV RNA IU/mL is less than LLOQ of the assay, the result is reported as “< 15 IU/mL HCV RNA detected”. This result will be referred to in this document as “< LLOQ detected”.

The overall category of HCV RNA < LLOQ includes “< LLOQ TND” and “< LLOQ detected.”

For numerical HCV RNA data, values below LLOQ will be set to the LLOQ – 1 IU/mL (ie, 14 HCV RNA IU/mL). HCV RNA values returned as “No HCV RNA detected” will also be set to 14 IU/mL.

If methods based on the assumption that the data are normally distributed are not adequate, analyses may be performed on transformed data (eg, log₁₀ scale) or nonparametric analysis methods may be used, as appropriate.

Natural logarithm transformation will be used for plasma/blood concentrations and analysis of PK parameters. Plasma concentration values that are below the lower limit of quantitation (BLQ) will be presented as “BLQ” in the concentration data listing. Values that are BLQ will be treated as 0 for determination of summary and order statistics and will be excluded in any calculation of geometric means or ratios.

For the presentation of summary and order statistics, if at least 1 subject has a concentration value of BLQ for the time point, then the minimum value will be displayed as “BLQ”. If more than 25% of the subjects have a concentration data value of BLQ for a given time point, then the minimum and Q1 values will be displayed as “BLQ”. If more than 50% of the subjects have a concentration data value of BLQ for a given time point, then the minimum, Q1, and median values will be displayed as “BLQ”. If more than 75% of the subjects have a concentration data value of BLQ for a given time point, then the minimum, Q1, median, and Q3 values will be displayed as “BLQ”. If all subjects have concentration data values of BLQ for a given time point, then all order statistics (minimum, Q1, median, Q3, and maximum) will be displayed as “BLQ”.

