4.2. Inclusion Criteria

Subjects must meet *all* of the following inclusion criteria to be eligible for participation in this study.

- 1) Parent or legal guardian able to provide written informed consent prior to any screening evaluations and willing to comply with study requirements. Subjects will provide assent if possible.
- 2) 3 years to < 18 years of age as determined at Day 1 (consent of parent or legal guardian required)
- 3) PK Lead-in phase only: subjects in Cohort 1 (age 12 to <18 years of age) must weigh ≥ 45 kg
- 4) PK Lead-in phase only: subjects in Cohort 2 (age 6 to <12 years of age) must weigh ≥ 17 kg and < 45 kg
- 5) PK Lead-in phase only: all subjects must be treatment naïve: no prior exposure to any IFN, RBV, or other approved or experimental HCV-specific DAA agent
- 6) Treatment experienced subjects: prior treatment failure to a regimen including interferon either with or without RBV that was completed at least 8 weeks prior to Day 1.
 - i) Interferon intolerant: Subject who discontinued therapy (≤ 12 weeks total) due to ≥ 1 adverse event
 - ii) Interferon non-responder: Subject who did not achieve undetectable HCV RNA levels while on treatment
 - iii) Relapse/breakthrough: Subject who achieved undetectable HCV RNA during treatment or within 4 weeks of the end of treatment but did not achieve a sustained virologic response (SVR)

- 7) Chronic HCV-infection documented by either:
 - a) a positive anti-HCV antibody test or positive HCV RNA or positive HCV genotyping test at least 6 months prior to the Day 1 visit, or
 - b) a liver biopsy performed prior to the Day 1 visit with evidence of chronic HCV-infection
- 8) Infection with HCV as determined at Screening:
 - a) United Kingdom Only: As of Protocol Amendment 4.0, the study is enrolling GT-1, -3, -4, -5, and -6 HCV-infected pediatric subjects and will subsequently enroll subjects with GT-2 once adult data is available, if appropriate.
 - b) United States/ Australia/ New Zealand Only: As of Protocol Amendment 4.0, the study is enrolling GT-1, -4, -5, and -6 HCV-infected pediatric subjects and will subsequently enroll subjects with GT-2 once adult data is available, if appropriate.
- 9) HCV RNA \geq 1000 IU/mL at Screening
- 10) Adequate hematologic function (absolute neutrophil count \geq 1,500/mm³; hemoglobin \geq 11 g/dL or \geq 12 g/dL for GT-3 males only).
- 11) Negative serum β -HCG pregnancy test (for females of childbearing potential only, as defined in [Appendix 5](#))

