1.2. Study Design

This is an open-label, multi-cohort, two-part study evaluating the PK, safety, and efficacy of LDV/SOF FDC ± RBV in chronic HCV-infected pediatric subjects.

The study will enroll both treatment-naïve and treatment-experienced pediatric subjects with up to 40 subjects allowed to be treatment experienced. Approximately 220 total subjects will be enrolled as follows:

- Approximately 100 adolescents aged 12 to < 18 years
- Approximately 120 children aged 3 to < 12 years

Subjects of 3 age groups will be enrolled in a sequential fashion: 12 to <18 years old, followed by 6 to <12 years old, and 3 to <6 years old.

Eligible subjects will receive the following treatment regimens based on HCV genotype, prior treatment experience, cirrhosis status and country of enrollment:

Table 1-1. Subject Enrollment by HCV Genotype, Country, and Treatment Duration

	GT1, GT4, GT5, & GT6		GT1	GT4, GT5, & GT6	GT3
	Cirrhotic or Non-cirrhotic Subjects (TN)	Non - cirrhotic Subjects (TE)	Cirrhotic Subjects (TE)	Cirrhotic Subjects (TE)	Non-cirrhotic or Cirrhotic Subjects (TE)
United States, Australia, New Zealand	12 Weeks of treatment with LDV/SOF FDC	12 Weeks of treatment with LDV/SOF FDC	24 Weeks of treatment with LDV/SOF FDC	12 Weeks of treatment with LDV/SOF FDC	N/A
United Kingdom				24 Weeks of treatment with LDV/SOF FDC	24 Weeks of treatment with LDV/SOF FDC + RBV

TN = Treatment Naïve, TE = Treatment Experienced, N/A = Not Applicable

Therefore, subjects actually enrolled are grouped into the treatment groups according to their age groups, HCV genotype, prior treatment experience, cirrhosis status, and treatment duration, as specified in Section 3.2.

The schedules of assessments for the study are provided as appendixes to the SAP (see Study Procedures Table, [Appendix 1](#)).

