3.2. Subject Grouping

For analyses based on the All Enrolled Analysis Set or FAS, subjects will be grouped according to the treatment to which they were enrolled. For analyses based on the Safety Analysis Set, subjects will be grouped according to the actual treatment received. The actual treatment received is defined as the enrolled treatment except for subjects who received treatment that differs from the enrolled treatment for the entire treatment duration. In this case, the actual treatment received is defined as the treatment received for the entire treatment duration.

Generally, subjects are analyzed, except for the safety analysis, by treatment groups based on age group, HCV genotype, prior treatment experience, cirrhosis status, and treatment duration:

Table 3-1. Non-safety Treatment Groups*

12 to < 18 Years Old		3 to < 12 Years Old			
LDV/SOF (90/400 mg) 12 Weeks		LDV/SOF (45/200 mg or 33.75/150 mg) 12 Weeks		LDV/SOF (45/200 mg) 24 Weeks	LDV/SOF+RBV (45/200 mg) 24 Weeks
GT1 TN w/ or w/o cirrhosis (N =)	GT1 TE without cirrhosis (N =)	GT1, GT4 TN w/ or w/o cirrhosis (N =)	GT1 TE without cirrhosis (N =)	GT1 TE with cirrhosis (N =)	GT3 TE w/ or w/o cirrhosis (N =)
6 to < 12 Years Old			3 to < 6 Years Old		
LDV/SOF (45/200 mg) 12 Weeks		LDV/SOF (45/200 mg) 24 Weeks	LDV/SOF+RBV (45/200 mg) 24Weeks	LDV/SOF (45/200 mg or 33.75/150 mg) 12 Weeks	
GT1, GT4 TN w/ or w/o cirrhosis (N =)	GT1 TE without cirrhosis (N =)	GT1 TE with cirrhosis (N =)	GT3 TE w/ or w/o cirrhosis (N =)	GT1, GT4 TN w/ or w/o cirrhosis (N =)	

GT = genotype, TN = Treatment Naïve, TE = Treatment Experienced, w/ = with, w/o = without
 *Treatment Groups reflect the subjects actually enrolled.

For the safety analysis, subjects will be analyzed by the following groups based on age group, treatment regimen and duration:

Table 3-2. Safety Treatment Groups

12 to < 18 Years Old	3 to < 12 Years Old		
LDV/SOF (90/400 mg) 12 Weeks (N =)	LDV/SOF (45/200 mg or 33.75/150 mg) 12 Weeks (N =)	LDV/SOF (45/200 mg) 24 Weeks (N =)	LDV/SOF+RBV (45/200 mg) 24 Weeks (N =)
6 to < 12 Years Old			3 to < 6 Years Old
LDV/SOF (45/200 mg) 12 Weeks (N =)	LDV/SOF (45/200 mg) 24 Weeks (N =)	LDV/SOF+RBV (45/200 mg) 24 Weeks (N =)	LDV/SOF (45/200 mg or 33.75/150 mg) 12 Weeks (N =)

Subjects in the 3 to < 6 years of age group will have additional selected efficacy and safety analyses performed according to baseline weight in the following subgroups:

Table 3-3. Subgroups for Selected Analyses in 3 to < 6 years of Age

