7.4. Body Weight, Height and BMI

An age- and sex-specific percentile will be derived for each weight, height and BMI measurement according to the downloadable SAS program available on the Centers for Disease Control (CDC) website using the year 2000 growth charts. Methods and SAS program published on the following CDC website will be applied to calculate the percentile {Centers for Disease Control and Prevention (CDC) 2016a, Centers for Disease Control and Prevention (CDC) 2016b}.

Body weight, height, BMI and percentiles for body weight, height, BMI at each visit, and change from baseline at each visit will be summarized for the Safety Analysis Set using descriptive statistics (n, mean, SD, median, Q1, Q3, minimum, and maximum) by treatment group.

In the case of multiple values in an analysis window, data will be selected for analysis as described in Section 3.7.3 (Selection of Data in the Event of Multiple Records in a Window). No inferential statistics will be generated.

A by-subject listing of body weight, weight percentile, height, height percentile, BMI and BMI percentile will be provided by subject ID number and visit in chronological order.

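### Filling an unknown birth day and month with 01 January can only overstate decimal age, by 0.5 year on average; a mid-year date removes this at almost no cost

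*SAP*

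**What the plan says.** SAP 3.6 uses "Age (in years) on the date of the first dose of study drug" for analyses and listings. A birthday that is missing is replaced by the first day of the year, a date that "will be used for the unknown birth day and month for the purpose of age calculation". Two conditions limit this. One is what the form records in a given country: "For some countries, only birth year is collected on the eCRF". The other is an exception to the imputation, which the SAP words as "unless age is captured on the eCRF". The rule is therefore a fallback with two conditions: birth year only, and no age on the form.

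Age then matters in several places:

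- **SAP 7.4:** "An age- and sex-specific percentile will be derived for each weight, height and BMI measurement". The section does not name the age variable or its source.
- **SAP 5.1:** age is summarised within each age group, including minimum and maximum.
- **SAP 5.2:** the Schwartz constant for eGFR is 0.55 for children under 12 and for adolescent females, and 0.70 for males from 12 years.

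The age bands are "12 to <18 years old, followed by 6 to <12 years old, and 3 to <6 years old" (SAP 1.2). Eligibility requires "3 years to < 18 years of age as determined at Day 1" (Protocol 4.2). For the All Enrolled and Full Analysis Sets, SAP 3.2 states that "subjects will be grouped according to the treatment to which they were enrolled". The Safety Analysis Set is grouped by treatment actually received.

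**The concern.** A missing birthday can be filled with a date that is right on average or with one at the edge of what is possible. 01 January is at the edge, so the errors cannot cancel across children.

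The effect of treatment on growth and development is a secondary objective, and height and weight are secondary safety endpoints (Protocol 9.1.3). The trial has no control arm that would carry the same error. The percentiles compare each child with an external growth chart, so an overstated age makes a growing child look short and light for age. That is the direction a reader of the safety tables would be watching for.

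**Working it through.** The documents give no figure for the age error, so there is nothing of the plan's own to reproduce.

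**Inputs from the documents.** Imputed date 01 January and its exception (SAP 3.6); band limits 3, 6, 12 and 18 years (SAP 1.2); Schwartz constants 0.55 and 0.70 (SAP 5.2).

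**Assumptions, not in the documents.** Birthdays uniform over the year; for displayed ages, true age uniform within each band and first doses spread evenly over the calendar year; for the percentile illustration, height velocity 5 to 7 cm/year and height SD 5 to 6 cm at a given age.

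**1. Error in decimal age.** Error = true birth date minus 01 January of the same year.
- Range 0 to 364 days, never negative.
- Mean = (0 + 364)/2 = 182 days; 182/365.25 = 0.50 year.

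**2. Error in completed years.** If a fraction f of the calendar year has passed at first dose, a share 1 − f of affected children come out one year too old and the rest have no error.
- This is 90% at f = 0.1, 50% at f = 0.5 and 10% at f = 0.9.
- The average over the year is 50%, so the mean error is again 0.5 year.

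**3. Effect on a group's mean age.** Shift = 0.5 × share affected: 0.025 year at 5%, 0.05 at 10%, 0.125 at 25%, and 0.5 at 100%. The share is unknown.

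**4. Height percentile, if imputed decimal age is used.** For a truly median child at the mean error, z = −0.5 × velocity/SD.
- 5 cm/year, SD 6 cm: z = −0.42, the 33.8th percentile.
- 7 cm/year, SD 5 cm: z = −0.70, the 24.2nd percentile.
- The shift shrinks toward zero as growth slows.

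**5. Displayed age beyond the upper limit of the band.** Share of affected children = mean error/band width.
- 3 to <6 years: 0.5/3 = 16.7%.
- 6 to <12 and 12 to <18 years: 0.5/6 = 8.3% each. In the oldest band this means a displayed age of 18 or more.
- None fall below a lower limit. A simulation of 2,000,000 children per band gave 16.65%, 8.34% and 8.32%.

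**6. Schwartz constant.** 0.70/0.55 = 1.27. A boy just under 12 whose imputed age is 12 or more would have his baseline eGFR overstated by 27%, if imputed age is used there.

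**7. The same checks with 01 July (unbounded).**
- Error range −181 to +183 days, mean +1 day (0.003 year), mean absolute error 0.25 year.
- Displayed age outside the band: 4.2% up and 4.1% down for 3 to <6 years; about 2.1% up and 2.0 to 2.1% down in each six-year band.
- The bound proposed below brings these shares to zero. It can always be met, because an eligible child's true birthday lies in the birth year and puts the child in the band.

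**The case against.** The strongest reply is that the rule may never be used. It applies only when age is also absent from the eCRF. No birth-year-only country is identified among the four in SAP Table 1-1, and Protocol 10.1.4 allows date of birth on forms sent to the sponsor. This stands: the number affected is unknown and may be zero.

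Several stronger conclusions are tempting, but the documents do not support them:

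- **Children are analysed in the wrong age group.** Eligibility age is set at Day 1, and analysis groups follow enrolled or received treatment. Nothing in the SAP rebuilds age groups from imputed age. The 17% and 8% above concern displayed age only.
- **Every affected child is too old.** In completed years about half have no error, and SAP 3.6 does not say which form of age is meant.
- **All growth percentiles fall.** BMI need not rise with age, so its direction is open. Some subjects may be at Tanner 5 on Day 1 (Protocol 6.6.4), and the assumed height velocity need not hold for them.
- **The error would pass for a drug effect on growth.** Raw height and weight do not use age. The same age error applies at baseline and at follow-up, so it largely cancels in percentile change, and a low percentile before dosing is not a treatment effect.
- **Bone age is distorted.** SAP 7.6 summarises bone age and its change, with no comparison to chronological age.

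The exception for captured age does not settle the matter for percentiles. SAP 3.6 defines age at first dose, while SAP 7.4 needs an age at every measurement, and it gives no rule for later visits. If a captured age in completed years were treated as exact, the error would average −0.5 year, in the opposite direction.

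**Conclusion.** The point holds in a limited form. Where the fallback applies, 01 January overstates decimal age by 0 to 1 year, 0.5 year on average under uniform birthdays, and a mid-year date removes the mean error and halves the mean absolute error.

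The consequence is conditional. If this age feeds SAP 7.4, the height and weight percentiles of affected growing children are biased downward at each visit. Under the assumed velocities and SDs, a median child would appear at roughly the 24th to 34th height percentile. Displayed ages outside the enrolled band and a wrong Schwartz constant for some boys near 12 are possible side effects. SVR12 and the treatment grouping are not shown to be affected. Severity is low.

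**What to change.** In SAP 3.6, replace 01 January with 01 July. If that date puts age at first dose outside the band in which the child was enrolled, move it to the nearest date in the birth year that keeps the child in the band.

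Use this one birth date for the age behind the percentiles at each visit (SAP 7.4) and for the 12-year cut-off of the Schwartz constant (SAP 5.2), and say so in both sections. Report the number of subjects whose birth date was imputed.

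Using captured age where available and grouping by enrolled treatment are already in the SAP and need no change. The cost is one date constant and one bound in the derivation program, plus a few sentences in the SAP. No new data are needed.
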